498 about the details regarding authorization.

499 A participant is considered enrolled when the informed consent form and child assent (if
500 applicable) has been signed.

501 **2.2 Participant Inclusion Criteria**

502 Individuals must meet all of the following inclusion criteria in order to be eligible to participate in
503 the study.

504 1. Clinical diagnosis, based on investigator assessment, of type 1 diabetes for at least one year
505 and using insulin for at least 6 months

506 2. Familiarity and use of a carbohydrate ratio for meal boluses.

507 3. Age \geq 6 and \leq 13 years old

508 4. Weight \geq 25 kg and \leq 140 kg

509 5. For females, not currently known to be pregnant

510 *If female and sexually active, must agree to use a form of contraception to prevent pregnancy
511 while a participant in the study. A negative serum or urine pregnancy test will be required for
512 all females of child-bearing potential. Participants who become pregnant will be discontinued
513 from the study. Also, participants who during the study develop and express the intention to
514 become pregnant within the timespan of the study will be discontinued.*

515 6. Living with one or more parent/legal guardian knowledgeable about emergency procedures for
516 severe hypoglycemia and able to contact emergency services and study staff.

517 7. Willingness to suspend use of any personal closed loop system that they use at home for the
518 duration of the clinical trial once the study CGM is in use

519 8. Investigator has confidence that the participant can successfully operate all study devices and
520 is capable of adhering to the protocol

521 9. Willingness to switch to lispro (Humalog) or aspart (Novolog) if not using already, and to use
522 no other insulin besides lispro (Humalog) or aspart (Novolog) during the study for participants
523 using the t:slim X2. This includes:

524 ○ Participants randomized to Control IQ

525 ○ Participants on the SC group on MDI treatment that will be provided a Tandem
526 pump to switch to CSII

527 ○ Participates that are already in CSII randomized to SC during the extension phase
528 when transition to Control IQ

529 10. Total daily insulin dose (TDD) at least 10 U/day

530 11. Willingness not to start any new non-insulin glucose-lowering agent during the course of the
531 trial (see section 2.3)

532 12. Participant and parent(s)/guardian(s) willingness to participate in all training sessions as
533 directed by study staff.

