760 CGM training will include:

- 761 • The participant will be instructed and supervised on how to insert the sensor and transmitter.
- 762 • The participant will learn how to calibrate the CGM unit
- 763 • The participant will learn how to access the CGM trace via the t:slim X2 with Control-IQ user
764 interface
- 765 • Participants will be asked to perform fingerstick blood glucose measurements in accordance
766 with the labeling of the study CGM device

767 Pump training will include:

- 768 • The participant will be fully instructed on the study insulin pump. A qualified system trainer
769 will conduct the training and in particular discuss differences from their home pump in
770 important aspects such as calculation of insulin on board and correction boluses. Additional
771 topics not limited to but may include: infusion site initiation, cartridge/priming procedures,
772 setting up the pump, charging the pump, navigation through menus, bolus procedures including
773 stopping a bolus, etc.
- 774 • The study team will assist the participant in study pump infusion site initiation and will start
775 the participant on the study pump. The study pump will be programmed with the participant's
776 usual basal rates and pump parameters. The participant's personal pump will be removed.
- 777 • The participant will be supervised with the study pump during at least one meal or snack bolus
778 to ensure participant understanding of the pump features.
- 779 • The participant will be encouraged to review the literature provided with the pump and infusion
780 sets after the training is completed.

781 Pump training specific to the Control-IQ Technology functions will include:

782 • How to turn on and off Control-IQ technology.

783 • How to understand when Control-IQ is increasing or decreasing basal rates.

784 • How to administer a meal or correction bolus on the t:slim X2 with Control-IQ system

785 • What to do when exercising while using the system

786 • How to enable the sleep function and set the sleep schedule

787 • The participant will be assessed for understanding of the system interface and how to react to

788 safety/alert messages.

789 • The participant will be given a User Guide as a reference.

790 **5.2.1 System Initiation**

791 The participant will be instructed to use the system in closed-loop mode except 1) when no

792 calibrated CGM sensor is available or 2) if insulin is delivered by any means other than the

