820 or <70 mg/dL or ketones ≥ 1.5 mmol/L.

821 **5.2.2 Home Use of the Study System**

822 After training on the study system has been completed, participants will proceed with home use
823 (meaning free-living use at school, home, etc.) of the t:slim X2 with Control-IQ technology
824 system.

825 Participants may use available manufacturer-provided software and features of the study CGM
826 related to mobile data access or remote monitoring, but will be instructed not to use any third-party
827 components for this purpose.

828 **5.2.3 Study Device Download**

829 Participants will be instructed to download the study device prior to each phone visit or on at least
830 every 3-week basis throughout the remainder of the study.

831 **5.2.4 1-Week Phone Contact**

832 Study staff will perform a phone call with the participant within 7 (± 1) days following
833 randomization.

834 The following will occur:

- 835 • Assessment of compliance with study device use by review of any available device data
- 836 • Assessment of adverse events, adverse device effects, and device issues
- 837 • Study staff will answer any questions related to device use

838 Participants will then complete an additional week of home use with the study system. Participants
839 will return to clinic 14 (± 3) days from the date of randomization.

840 **5.2.5 2-Week Visit (Training Review and Insulin Pump Optimization)**

841 The participant will be offered review training to address any questions on the use of the study
842 device including meal bolus strategies and strategies related to pump use and exercise.

843 The following will occur:

- 844 • Assessment of compliance with study device use by review of any available device data
- 845 • Assessment of adverse events, adverse device effects, and device issues
- 846 • Study staff will answer any questions related to device use and follow the procedure for insulin
847 pump optimization described in section 3.6 using the study CGM available data from the
848 previous two weeks.
- 849 • The blood glucose meter and study ketone meter will be downloaded and QC tested with
850 control solution.

851 **5.3 Procedures for the SC Group**

852 Participants in the SC group will use an insulin pump that they usually use for the treatment of
853 their diabetes or a study pump provided by the study team if they are transitioning from MDI to
854 pump for the study, in conjunction with the study CGM, study blood glucose meter, and study

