888 The schedule for remaining follow-up visits and phone contacts is the same for both treatment
889 groups. Study staff will discuss with the participant that periodic contact is required and will make
890 arrangements with the participant for the contacts. If the participant or parent/guardian, cannot be
891 reached, the participant's other contact methods will be utilized, including the emergency contact.

892 **5.4.1 Follow-up Visits**

893 Follow-up visits in clinic will occur at:

- 894 • 2 week (± 3 days)
- 895 • 8 weeks (± 1 week)
- 896 • 16 weeks (+1 week) – end of Main Study Phase

897 **5.4.1.1 Procedures at Follow-up Visits**

898 Procedures performed in both groups at each visit, unless otherwise specified below:

- 899 • Assessment of compliance with study device use by review of any available device data
- 900 • Assessment of adverse events, adverse device effects, and device issues
- 901 • Download of device data (study system or personal pump and study CGM, study BG meter,
902 study ketone meter)

903 **5.4.2 Phone Contacts**

904 In addition to the 1-week phone contact described above for the respective treatment groups, the
905 following phone contacts will be made:

- 906 • 4 weeks (± 3 days)
- 907 • 6 weeks (± 3 days)
- 908 • 10 weeks (± 3 days)
- 909 • 12 weeks (± 3 days)
- 910 • 14 weeks (± 3 days)

911 At each phone contact, the following procedures are performed in both treatment groups:

- 912 • Review of available CGM and/or system data to identify any safety issues associated with
913 insulin pump settings and current diabetes management approach
- 914 • Assessment of adverse events, adverse device effects, and device issues

915 Additional phone contacts may be performed as needed.

916 **5.4.3 Data from Study Devices**

917 All participants will be asked to upload data from the CGM at least once every 4 weeks during the
918 extension phase. The study staff will confirm that the data were received.

919 **5.4.4 16-Week Final First Phase Visit**

920 All participants will return to the clinic for a 16-Week (+7 days) final clinic visit during which the
921 following will occur:

- 922 • HbA1c determination using the DCA Vantage or similar point of care device
- 923 • Collection of a blood sample to send to the central laboratory for HbA1c determination
- 924 • Completion of questionnaires
- 925 • Weight and height measurement will be repeated
- 926 • Assessment of adverse events, adverse device effects, and device issues

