149 calculate overnight metrics. If <168 hours of CGM data available for combined day and night,
150 then CGM metrics will not be calculated separately for daytime and overnight periods.
- 151 • CGM metrics by 4-week periods: Starting from the randomization date, CGM metrics will be
152 calculated within each 4-week period (Week 1-4, Week 5-8, Week 9-12 and Week 13-16). The

153 16 weeks visit date will be used as end date of Week 13-16. Minimum 168 hours of CGM data in
154 each 4-week period will be required for the calculation.

155 • CGM metrics by 1-week periods: Starting from the randomization date, CGM metrics will be
156 calculated within each 1-week period. The 16 weeks visit date will be used as end date of Week
157 13-16. Minimum 132 hours of CGM data in each 1-week period will be required for the
158 calculation.

159
160 **4.4 Calculation of Insulin Metrics**

161 • Insulin metrics will be calculated at randomization and 16 weeks using Tandem pump data
162 where available, otherwise using data reported on the CRF.
163 • Insulin metrics will be calculated from the pump data using data in the 7 days prior to the visit.

164
165 **4.5. Questionnaires**

166 All questionnaires will be administered online and participants/parents can skip specific questionnaires
167 or items within a questionnaire. All questionnaires will be scored according to the instructions given in
168 the manual. In case no manual exists for a given questionnaire or the manual does not provide guidance
169 on how to handle missing data, then the following criteria will be applied:

170 • At least 75% of the questions must be completed to be included in the analysis.
171 • This 75% rule will be applied separately for the total score and each subscale so it is possible the
172 sample size will be different for some subscales.
173 • The score used for analysis will be based on the average among the questions that were answered
174 and then scaled accordingly.

175 **4.6 Analysis Windows**

176 Analysis windows apply to the following outcomes measured at 16 week visit:

177 • HbA1c
178 • Insulin metrics if calculated from CRF data
179 • Weight/BMI
180 • Questionnaires

181
182 This does not apply to the CGM metrics which are calculated as described above.

183
184 Data from 16 weeks visit occurring in the following windows will be included in analysis:

Visit (Target Date)	Metrics ^a	From Day ^b	Thru Day ^b
16 weeks (112 days)	H,I,B,Q	98	126

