185 a – H = HbA1c, I = Insulin metrics, B=BMI (and weight), Q = Questionnaires.

186 b – Days from randomization, inclusive.

187
188 **5. Analysis Datasets and Sensitivity Analyses**

189 **5.1 Analysis Datasets**

190 All analyses comparing the CLC arm with SC arm will follow intention-to-treatment approach, which
191 means participants will be analyzed in the treatment arm assigned by randomization regardless of
192 compliance. All randomized participants will be included in the primary analysis and secondary

193 hierarchical analyses of CGM metrics. For other secondary outcomes, only participants with non-
194 missing outcome data will be included.

195 Safety outcomes will be reported for all enrolled participants, irrespective of whether the participants
196 was randomized or the study was completed.

197 **5.2 Sensitivity Analyses**

198 The following sensitivity analyses (except for the per-protocol analyses) will be conducted for primary
199 endpoint only.

200 *Per Protocol (PP) Analyses:*

201 The following per-protocol analyses will be performed for the primary outcome and secondary
202 hierarchical outcomes only if >5% of participants will be excluded:

- 203 • CLC group: Closed loop mode active for at least 80% of the time
- 204 • SC group: CGM use for at least 80% of the time

205 *Confounding:*

206 A sensitivity analysis will also be conducted if potential confounding factors collected at baseline are
207 detected. The baseline factors listed in Section 11 will be assessed for imbalance between treatment
208 groups.

209 The imbalance will be assessed based on clinical judgement reviewing the distributions in the two
210 treatment arms, not on a p-value. The person making this judgement will be unaware of whether there is
211 an association between baseline variables and study outcome. All variables obtained on a continuous
212 scale will be entered into the models as continuous variables, unless it is determined that a variable does
213 not have a linear relationship with the outcome. In such a case, categorization and/or transformation will
214 be explored.

216 *Exclude First 2 Weeks of CGM Data*

217 The primary analysis will be repeated by excluding the first 2 weeks of post-randomization CGM data.

218 *Missing Data:*

219 Missing data will be handled using direct likelihood method for the primary analysis. It is worth noting

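### At week 16 the SAP's source rule measures insulin use from pump downloads in the CLC arm but partly from the CRF in the SC arm

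*SAP*

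**What the plan says.** SAP 4.4 gives the rule: "Insulin metrics will be calculated at randomization and 16 weeks using Tandem pump data" "where available, otherwise using data reported on the CRF". It sets a 7-day look-back for values taken from the pump. It does not say how a CRF value is obtained or what period it covers, and the protocol does not say so either.

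The protocol ties pump brand to arm after randomization:

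- **CLC (Protocol 5.2).** The participant starts the study t:slim X2, and the "personal pump will be removed".
- **SC (Protocol 5.3).** "Participants in the SC group will use an insulin pump that they usually use for the treatment of" their diabetes. The exception is those coming from injections, who receive a study pump.
- **SC from injections (Protocol 2.2, criterion 9).** That study pump is a Tandem: "Participants on the SC group on MDI treatment that will be provided a Tandem" pump. The same criterion has SC participants already on a pump using the t:slim X2 only from the extension phase.

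Total daily insulin (units/kg) and the basal:bolus ratio are listed in SAP 4.2.2 among endpoints labelled exploratory. SAP 6.2.2 compares them between arms in a linear model with baseline value, age, prior CGM and pump use, and center. SAP 14 places insulin with weight and BMI in one FDR family. SAP 15 applies the 4.4 data to further by-arm tables of basal, bolus, manual bolus and automated bolus insulin, without p-values.

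**The concern.** The rule names one brand, and which brand a participant wears at week 16 depends partly on the assigned arm. One arm is then measured almost wholly by device log. Part of the other is measured by a form entry of undefined origin. If form entries run systematically higher or lower than logs, the difference would be read as an effect of closed-loop control on insulin use, in either direction.

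Nothing in the planned analysis would reveal or remove it. The model has no term for source, and such a term would be largely confounded with arm. SAP 5.2 limits the sensitivity analyses to the primary endpoint and the per-protocol analyses to the primary and hierarchical endpoints, so neither covers insulin.

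**Working it through.** The plan states no figure on this point, so there is none to reproduce. The check has three steps.

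**1. Who is scored from what at week 16**

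| Group | Pump at week 16 | Source under SAP 4.4 |
|---|---|---|
| CLC, any prior treatment | Study Tandem | Download |
| SC, previously on injections | Study Tandem | Download |
| SC, owns a Tandem | Own Tandem | Download |
| SC, owns another brand | Own pump | CRF |

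A few CLC participants may lack Tandem data, through a missing download or because they stopped the device and stayed in the study (Protocol 9.5.1).

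**2. Does baseline adjustment remove the difference?**

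The baseline source is settled before assignment, so its mix is balanced between arms in expectation. The protocol is unclear about which source other-brand users have at baseline. Section 3.1 sends those naïve to the study pump into the pump run-in, while 3.3 speaks only of pump-naïve participants. Take owners of another brand under each reading:

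- No pump run-in: CLC goes from CRF to download; SC stays on CRF.
- Pump run-in on the study Tandem: CLC stays on download; SC goes from download to CRF.

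In both cases the arms match at baseline and differ at week 16 by one source gap. Adjusting for a baseline that is balanced in expectation leaves that gap in place.

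**3. Size**

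Let μ be the common true mean with no treatment effect, g the proportional CRF-versus-download gap, and s the share of an arm scored from the CRF. Assume CRF-scored participants have the same true mean as the rest of their arm. Then:

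- measured mean in an arm = μ(1 + s·g)
- SC minus CLC = μ·(s_SC − s_CLC)·g = μ·f·g

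The bias as a share of the SC mean is therefore about f × g.

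Inputs from the documents: 100 randomized at 3:1 gives 100 × 1/4 = 25 SC and 75 CLC. Protocol 2.1 aims for at least 20% on injections. At exactly 20% in the SC arm, 25 × 0.20 = 5 are on a study Tandem and 20 keep their own pump. The Tandem share among those 20 is not given. Taking s_CLC = 0 and assuming g = 5% or 10%:

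| Tandem share among 20 SC pump users | SC on CRF | f | Bias, g = 5% | Bias, g = 10% |
|---|---|---|---|---|
| 0% | 20 of 25 | 0.8 | 4% | 8% |
| 25% | 15 of 25 | 0.6 | 3% | 6% |
| 50% | 10 of 25 | 0.4 | 2% | 4% |
| 75% | 5 of 25 | 0.2 | 1% | 2% |
| 100% | 0 of 25 | 0 | 0% | 0% |

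The top row is an extreme: no SC pump user owns a Tandem and no CLC participant falls back on the CRF. For the basal:bolus ratio a gap common to both parts cancels, since basal(1+g) / bolus(1+g) equals basal / bolus. That endpoint is biased only if the two parts are off by different proportions.

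**The case against.** The strongest reply is that harm depends on a form not in the file. Personal pumps are downloaded at follow-up visits and at week 16 (Protocol 5.4.1.1 and 5.4.4), so staff could complete the CRF from the download. If they do so over the same 7 days, the gap could be close to zero. This stands as a limit on the claim. The documents show that the source differs by arm and that the CRF value is undefined. A reader might infer that the insulin comparison is therefore biased, but they do not show that.

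A reader might also want to turn f × gap into a false-positive rate. The documents do not support one. They give no size or sign for the gap, no SD for insulin in units/kg, and no baseline-to-follow-up correlation for the adjusted model.

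It can further be said that using other brands' files does not produce a single source, because pump logs may differ in how they record basal and bolus. That is true, and it remains as a cost of the fix. It does not favor an undefined form entry over a device record with a known period.

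Finally, SAP 4.6 might be read as contradicting itself on the insulin window, since its list says "Insulin metrics if calculated from CRF data" and its footnote says "I = Insulin metrics, B=BMI (and weight), Q = Questionnaires". The footnote only explains the table's letters, so there is no contradiction to pursue.

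**Conclusion.** The point holds as a minor defect in measurement. The SAP's own rule, combined with the protocol's pump assignment, makes the week-16 source of the insulin metrics differ by arm, and no planned analysis corrects for it. The bias lies between zero and, under the assumed 5–10% gap, 8% of the SC mean for total daily insulin. A value of 2–4% corresponds to 10 of 25 SC participants on the CRF. The direction is unknown. These figures rest on assumed gaps, an unknown share of Tandem owners in the SC arm, and a CLC arm scored wholly from downloads. If the sources agree, or if every SC pump user owns a Tandem, there is no bias.

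The reach is two exploratory endpoints with FDR-adjusted p-values, plus the by-arm insulin tables in SAP 15 that draw on 4.4.

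**What to change.** Three changes to the SAP:

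1. **Source.** In 4.4, calculate insulin metrics from 7-day pump downloads in both arms. Include the personal-pump downloads already collected under Protocol 5.4.1.1 and 5.4.4, and any available at randomization (Protocol Table 1 schedules device downloads from screening on). Use the CRF only where no file can be read, with a stated origin and the same 7-day look-back.
2. **Reporting.** Tabulate the source used, by arm and visit.
3. **Sensitivity analysis.** Repeat the two insulin comparisons in participants who at enrollment were on injections or used a personal Tandem. This subset is fixed before randomization, and both arms are expected to have Tandem data at week 16.

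The subset should be defined at enrollment. Defining it by the pump worn just before randomization could bring back the asymmetry: if users of another brand spend the run-in on the study pump, SC members return to their own pump afterwards. A subset with the same source at both visits would select differently by arm.

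The cost is SAP wording and processing of files already held. Some files may be unreadable, some brand differences between logs will remain, and the subset will be small: about 5 SC participants from injections at the 20% target, plus however many SC participants own a Tandem.
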